4.1 Adverse Events

4.1.1 Definition of Adverse Events

As defined by the ICH Guideline for Good Clinical Practice (CPMP/ICH/135/95), an AE is:

Any untoward medical occurrence in a subject or clinical investigations subject administered a pharmaceutical product and which does not necessarily have a causal relationship with this treatment.

An AE can therefore be any unfavorable and unintended sign (including an abnormal laboratory finding), symptom, or disease temporally associated with the use of a medicinal product, whether or not considered related to the medicinal product.

An AE includes but is not limited to:

- Any clinically significant worsening of a pre-existing condition;
- An AE occurring from overdose (ie, a dosage higher than that prescribed by a healthcare professional for clinical reasons, or a dosage higher than that described on the marketed product label) of an investigational or marketed product, whether accidental or intentional;
- An AE occurring from abuse (eg, use for nonclinical reasons) of an investigational or marketed product;
- Any laboratory abnormality that is judged by the investigator to be medically significant (except as noted in Section 4.10).
- An event related to a medical procedure or associated with the discontinuation of the previous use of an investigational or marketed product required by protocol (protocol-related AE).

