4.10 Definitions of Dose-limiting Toxicities

Dose-limiting toxicities will be graded according to the NCI CTCAE V3.0 and will be assessed during the first cycle of treatment with MEDI-573 (Cycle 1, Day 1 through Cycle 1, Day 21).

A DLT is defined as:

- 1) Any Grade 3 or higher non-hematologic toxicity that occurs during the DLT assessment period where a cause other than the investigational product (such as disease progression or accident) cannot be reasonably justified with the following exceptions:
 - Grade < 4 serum-high glucose (fasting) with duration of < 24 hours.
 - Grade 3 fever (in the absence of neutropenia) defined as > 40.0°C (>104.0°F) that resolves to normal or baseline within 24 hours of treatment and is not considered an SAE; or
 - Grade 3 rigors/chills that respond to optimal therapy.
- 2) Any Grade 3 or higher hematologic toxicity that occurs during the DLT assessment period where a cause other than the investigational product (such as disease progression or accident) cannot be reasonably justified.

5 Statistical Considerations

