5.3 Primary Endpoints

The primary objectives of this study are to evaluate the safety and tolerability of MEDI-573 in adult subjects with advanced solid tumors refractory to standard therapy or for which no standard therapy exists and to determine the MTD or OBED of MEDI-573 in this subject population. The OBED will be the dose at which all circulating IGF-1 and IGF-2 ligand is expected to be sequestered by MEDI-573, and will be based on pre-clinical data, PK/pharmacodynamic modeling, and pharmacodynamic analyses of circulating IGFs in representative samples of human blood collected in the dose-escalation phase of the study. All safety endpoints will be summarized descriptively. Adverse events and SAEs will be summarized by cohort, system organ class, severity, and relationship to MEDI-573 through 30 days after the last dose of MEDI-573. For assessment of the MTD, descriptive statistics will be provided to summarize the occurrence of DLTs by cohort.

Determination of the MTD or OBED is described in Section 4.9 and descriptive statistics will be provided to summarize the occurrence of DLTs by cohort.

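### Section 4.1.1 carries a DLT exception into the list of adverse events, so the AE status of transient fasting hyperglycemia below Grade 4 is contradictory and may be under-recorded

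*Protocol*

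**What the plan says.** Section 4.1.1 opens with the ICH definition, which counts as an AE "any unfavorable and unintended sign (including an abnormal laboratory finding), symptom, or disease temporally associated with the use of a medicinal product". A causal link to the product is not required. A list follows, introduced by "An AE includes but is not limited to". One entry in that list is "Any laboratory abnormality that is judged by the investigator to be medically significant (except as noted in Section 4.10", with the parenthesis closing there.

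Section 4.10 defines DLTs and says nothing about AE recording. Its first item covers non-hematologic toxicity of Grade 3 or higher "where a cause other than the investigational product (such as disease progression or accident) cannot be reasonably justified with the following exceptions". The first exception is "Grade < 4 serum-high glucose (fasting) with duration of < 24 hours". The other two concern fever and rigors or chills. DLTs "will be assessed during the first cycle of treatment with MEDI-573 (Cycle 1, Day 1 through Cycle 1, Day 21", where that parenthesis also closes.

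Section 5.3 states the primary safety analysis: "All safety endpoints will be summarized descriptively". For the tabulation of events it says: "Adverse events and SAEs will be summarized by cohort, system organ class, severity, and relationship to MEDI-573". The window for that tabulation closes 30 days after the final dose.

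**The concern.** An exception that settles whether an event counts toward the escalation rule has no evident reason to settle whether the event is an adverse event. By pointing to Section 4.10, the AE list appears to import that exception. An investigator could read it as permission not to record a short glucose elevation that he or she considers medically significant.

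Safety and tolerability is the first primary objective, and the AE and SAE tables by cohort are a main part of how it is answered. Hyperglycemia is a toxicity the protocol itself flags: Section 1.2 reports Grade 3 hyperglycemia, and a 10% rate of Grade 1 or 2 events in one study, with antibodies against the same pathway. Section 1.6 argues that neutralizing the ligands should leave insulin signaling and metabolism unaffected. For this toxicity, recording should not depend on which sentence of Section 4.1.1 a site follows.

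**Working it through.** The protocol gives no figure to reproduce. The check is a reading of the sections against each other, with one small piece of arithmetic on the sampling schedule.

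1. **What the parenthesis can refer to.** Section 4.10 has three exceptions: fasting glucose below Grade 4 for under 24 hours, certain Grade 3 fever, and Grade 3 rigors or chills that respond to therapy. Only the first is a laboratory abnormality, so it is the only one that an entry about laboratory abnormalities can take up. It sits under an item for Grade 3 or higher, so within Section 4.10 it operates on Grade 3.

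2. **What the exception does in its own section.** It qualifies the definition of a non-hematologic DLT, in Cycle 1, Days 1 to 21. The summary of amendments in Appendix 4 also describes the glucose item as an exception to the DLT criteria. Neither place mentions AE recording.

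3. **One event under each text.** Take a Grade 3 fasting glucose in Cycle 1 that lasts less than 24 hours and is judged medically significant.
   - General definition in 4.1.1: an AE, which Section 4.1.2 then requires to be reported.
   - List entry in 4.1.1, read literally: excepted.
   - Section 4.10: not a DLT, whichever answer is taken above.

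   The first two answers conflict. The third does not depend on them, so AE recording can be clarified without touching the DLT rule.

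4. **Where AE status matters.**
   - Section 5.3 tabulates what has been recorded as an AE or SAE.
   - Section 4.2.1 defines an SAE as a kind of AE, so AE status comes first.
   - Section 4.9 has treating investigators describe adverse events for the decision on the next cohort.
   - Section 4.9 also allows an intermediate expansion dose to be considered when toxicities fall short of a DLT. A short Grade 3 glucose elevation is a toxicity of that kind.

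5. **What is captured anyway.** Glucose is part of scheduled serum chemistry (Tables 3.6-1 and 3.6-2). In Cycle 1 it is drawn on Days 1, 3, 8 and 15 in Cohorts 1 to 5 and the expansion phase, and on Days 1, 3 and 8 in Cohorts 6 and 7. With Cycle 2 Day 1 on Day 22 (15 + 7, or 1 + 21), the gaps are:
   - Cohorts 1 to 5 and expansion: 3 − 1 = 2, 8 − 3 = 5, 15 − 8 = 7 and 22 − 15 = 7 days.
   - Cohorts 6 and 7: 2, 5 and 22 − 8 = 14 days.

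   Every gap exceeds 24 hours. An episode shorter than that is caught by the schedule only if it coincides with a draw; otherwise it reaches the data mainly through AE recording. A laboratory value also carries no investigator assessment of relationship, which Section 4.1.3 requires for AEs.

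6. **Size.** An estimate needs the rate of Grade 3 fasting hyperglycemia on MEDI-573, the share lasting under 24 hours, and the share of those that sites would leave unrecorded. The protocol gives none of the three.

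**The case against.** The strongest reply is that nothing is excluded. The general definition covers abnormal laboratory findings without qualification, the list is expressly not exhaustive, and dropping an example from such a list does not narrow the definition. This stands as far as it goes: a reader might infer that these episodes fall outside the AE definition, and the document does not support that. It does not remove the problem, because a specific written exception beside a general rule is a contradiction that sites can resolve in different ways.

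A second reply reads the parenthesis as widening capture: laboratory events that meet Section 4.10 would be AEs whatever the investigator's view of significance. Section 3.5.5, which requires every DLT to be documented as an AE, fits that reading. It is strained, however. The parenthesis is worded as an exception to what counts as an AE, and the exceptions in Section 4.10 are themselves exclusions.

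Third, a reader might infer that the carve-out applies in every cycle and in the expansion phase, because the parenthesis has no time limit. Section 4.10 confines its exceptions to the DLT assessment period in Cycle 1. Later toxicity is governed by Table 3.5.5-1 and Section 4.7, which contain no glucose exception. Wider reach is a possible reading and no more.

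Fourth, a reader might infer that the episodes vanish from the primary safety summaries or from safety oversight. That goes too far. Glucose is collected on schedule, HbA1c is measured at screening and end of treatment, and concomitant medications are recorded. Section 5.3 summarizes all safety endpoints, and Section 4.6 does not restrict the medical monitor or the Safety Monitoring Committee to recorded AEs.

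**Conclusion.** The point holds as a contradiction with a plausible route to inconsistent under-recording. It affects the AE/SAE tabulation and the AE descriptions used at escalation meetings, mainly for transient Grade 3 fasting hyperglycemia in Cycle 1. It rests on the natural reading of the parenthesis as an exclusion and on at least some sites following the specific entry over the general definition.

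No size can be attached. It is tempting to apply the 10% rate in Section 1.2 to the planned 41 to 62 subjects (21 to 42 in escalation plus about 20 in expansion), which would give 4.1 to 6.2 subjects. That figure does not measure this problem: the rate is for Grade 1 or 2 events, it comes from a receptor antibody rather than a ligand antibody, and it says nothing about duration. A reader might also infer a bias toward the Section 1.6 rationale. Under-recording would lean that way, but the document does not show that it would occur or how much would be lost.

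The matter is more than editorial because AE status feeds a primary objective and the escalation discussion for a toxicity the protocol itself cites. It is worth correcting, and it does not undermine the design.

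**What to change.** Delete the parenthesis referring to Section 4.10 from the laboratory entry in Section 4.1.1, so that every laboratory abnormality the investigator judges medically significant is recorded as an AE. Leave the exceptions in Section 4.10 as they are, where they limit DLT classification only. Remind sites that an event can be an AE without being a DLT.

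The change alters no dose, escalation criterion or treatment rule. It costs one deletion, the reminder to sites and a few more AE entries.

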4.1.2 Study Reporting Period for Adverse Events

All AEs that occur after a subject has received the investigational product through 30 days after the last dose of MEDI-573 must be reported by the investigator.

Any new sign or symptom, disease, or other untoward medical event that occurs after the subject/legal representative signs the informed consent form but before the subject has received investigational product, and which may possibly be causally related to the protocol (ie, results from a required procedure or from withdrawal of prior medication), must be reported by the investigator as an AE in the same way as AEs that occur after the subject receives investigational product.

4.1.3 Recording of Adverse Events

Adverse events will be reported using a recognized medical term or diagnosis that accurately reflects the event. AEs will be assessed by the investigator for severity, relationship to the investigational product, possible etiologies and whether the event meets criteria as a SAE and therefore requires immediate notification of the Sponsor. See Section 4.2.1 for the definition of SAEs, and Section 4.3 and Section 4.4 for guidelines for assessment of severity and relationship, respectively. If the event has not resolved at the end of the study reporting period it will be documented as ongoing. If an AE evolves into a condition which becomes “serious” it will be reported on the SERIOUS ADVERSE EVENT (SAE) REPORT FORM.

4.2 Serious Adverse Events

4.2.1 Definition of Serious Adverse Events

An SAE is any AE that:

- Results in death
- Is immediately life-threatening
- This term refers to an event in which the subject was at risk of death at the time of the event; it does not refer to an event that hypothetically might have caused death if it were more severe.
- Requires inpatient hospitalization or prolongation of existing hospitalization
- In general, hospitalization signifies that the subject has been detained (usually involving at least an overnight stay) at the hospital or emergency ward for observation and/or treatment that would not have been appropriate in an outpatient setting. Complications that occur during hospitalization are AEs. If a complication prolongs hospitalization or fulfills any other serious criteria, the event is serious. When in doubt as to whether “hospitalization” occurred or was necessary, the AE should be considered serious. Hospitalization for elective treatment of a pre-existing condition that did not worsen from baseline is not considered an AE.

- Results in persistent or significant disability/incapacity
- The term disability means a substantial disruption of a person's ability to conduct normal life functions. This definition is not intended to include experiences of relatively minor medical significance such as uncomplicated headache, nausea, vomiting, diarrhea, influenza, and accidental trauma (eg, sprained ankle) which may interfere or prevent everyday life functions but do not constitute a substantial disruption.
- Is a congenital anomaly/birth defect in offspring of the subject
- A pregnancy should be reported to MedImmune Patient Safety as an immediately reportable event (IRE). A pregnancy should be followed for outcome and the health status of the mother and the child. If the child is born with any congenital anomaly of birth defect, this should be reported to MedImmune Patient Safety as a SAE.
- Is an important medical event that may jeopardize the subject or may require medical intervention to prevent one of the outcomes listed above
- Medical or scientific judgment should be exercised in deciding whether expedited reporting is appropriate in this situation. Examples of medically important events are intensive treatment in an emergency room or at home for allergic bronchospasm, blood dyscrasias, or convulsions that do not result in hospitalizations; or development of drug dependency or drug abuse.
- A serious event related to a medical procedure required by protocol prior to dosing of the study medication should also be reported to MedImmune Patient Safety as a SAE (protocol-related SAE).

4.2.2 Study Reporting Period for Serious Adverse Events

The reporting period for SAEs is the period immediately following the time that written informed consent is obtained through 30 days after the last dose of MEDI-573. After the initial SAE report, the investigator is required to follow each subject proactively and provide further information on the subject's condition to MedImmune Patient Safety.

All SAEs should be followed up to resolution by the investigator, even if this extends beyond the study reporting period. Resolution of an SAE is defined as the return to baseline status or stabilization of the condition with the expectation that it will remain chronic.

At any time after completion of the study, if an investigator or qualified designee becomes aware of an SAE that is suspected by the investigator or qualified designee to be related to investigational product, the event should be reported to MedImmune Patient Safety.

4.2.3 Notification of Sponsor of Serious Adverse Events

Within 24 hours of identifying an SAE, regardless of the presumed relationship to the investigational product, the investigator or qualified designee must complete the SAE Report form and fax to MedImmune Patient Safety.

MedImmune contact information:

MedImmune Patient Safety
MedImmune
[name]
Gaithersburg, MD 20878
[contact]

MedImmune, as Sponsor of the study being conducted under an Investigational New Drug Application (IND), is responsible for reporting certain SAEs as IND safety reports to the FDA, other applicable regulatory authorities, and participating investigators, in accordance with the U.S. Code of Federal Regulations (21 CFR 312.32 and 312.33) ICH Guidelines, and/or local regulatory requirements. MedImmune may be required to report certain SAEs to regulatory authorities within 7 calendar days of being notified about the event; therefore, it is important that investigators submit additional information requested by MedImmune as soon as it becomes available.

Investigators should provide all available information at the time of form completion. Investigators should not wait to collect additional information to fully document the event before notifying MedImmune of an SAE. When additional information becomes available, submit a follow-up SAE report form with the new information. Any follow-up information to an SAE also needs to be provided to MedImmune Patient Safety within 24 hours of learning of the new information.

4.2.4 Notification of Institutional Review Board or Independent Ethics Committee of Serious Adverse Events

The investigator must comply with the applicable regulatory requirements related to the reporting of SAEs to the Institutional Review Board (IRB) or Independent Ethics Committee (IEC). The IRB or IEC must be informed in a timely manner by the principal investigator of serious AEs occurring at their site during the study. Investigators must also submit safety information provided by MedImmune to the IRB or IEC as detailed in Section [7.2](#).

4.2.5 Recording of Serious Adverse Events

Serious adverse events will be recorded on the SAE REPORT FORM using a recognized medical term or diagnosis that accurately reflects the event. SAEs will be assessed by the investigator for severity, relationship to the investigational product, and possible etiologies. See Section 4.2.1 for the definition of SAEs, and Section 4.3 and Section 4.4 regarding guidelines for assessment of severity and relationship, respectively.

For the purposes of study analysis, if the event has not resolved at the end of the study reporting period it will be documented as ongoing. For purposes of regulatory safety monitoring the investigator is required to follow the event to resolution and report to the Sponsor the outcome of the event using the SAE REPORT FORM.

4.3 Assessment of Severity

Assessment of severity is one of the responsibilities of the investigator in the evaluation of AEs and SAEs. The determination of severity should be made by a health care professional who is qualified to review AE information, provide a medical evaluation of AEs, and classify AEs based upon medical judgment and the severity categories of *Grade 1*, *Grade 2*, *Grade 3*, *Grade 4*, and *Grade 5*. Severity of toxicity will be graded according to the NCI CTCAE V3.0.

It is important to distinguish between serious and severe AEs. Severity is a measure of intensity whereas seriousness is defined by the criteria in Section 4.2.1. An AE of severe intensity need not necessarily be considered serious. For example, nausea that persists for several hours may be considered severe nausea, but not an SAE. On the other hand, a stroke that results in only a limited degree of disability may be considered a mild stroke, but would be an SAE.

AEs not described within the NCI CTC AE V3 will be reported using the severity categories as follows:

Grade 1:	Mild AE
Grade 2:	Moderate AE
Grade 3:	Severe AE
Grade 4:	Life-threatening or disabling AE
Grade 5:	Death related to AE

4.4 Assessment of Relationship

An AE is considered “product-related” for the purposes of regulatory reporting if the investigator, the medical monitor, or the patient safety physician assesses the AE as possibly, probably, or definitely related to investigational product. This is not a conclusive determination of causal association between the product and the event.

Whenever the investigator’s assessment is unknown or unclear, the AE is treated as product-related for the purposes of reporting to regulatory authorities. An AE may be deemed to be not related to the product for purposes of regulatory reporting only if the investigator, medical monitor, and patient safety physician, if applicable, agree that the AE is not product-related.

The investigator is required to provide an assessment of relationship of AEs and SAEs to the investigational product. A number of factors should be considered in making this assessment including: 1) the temporal relationship of the event to the administration of investigational product; 2) whether an alternative etiology has been identified; and 3) biological plausibility. The following guidelines should be used by investigators to assess the relationship of an AE to investigational product administration.

Relationship assessments that indicate an “Unlikely Relationship” to investigational product:

None: The event is related to an etiology other than the investigational product (the alternative etiology must be documented in the study subject’s medical record).

Remote: The event is unlikely to be related to the investigational product and likely to be related to factors other than investigational product.

Relationship assessments that indicate a “Likely Relationship” to investigational product:

Possible: There is an association between the event and the administration of the investigational product and there is a plausible mechanism for the event to be related to investigational product; but there may also be alternative etiology, such as characteristics of the subject’s clinical status or underlying disease.

Probable: There is an association between the event and the administration of investigational product, a plausible mechanism for the event to be related to the investigational product and the event could not be reasonably explained by known characteristics of the subject's clinical status or an alternative etiology is not apparent.

Definite: There is an association between the event and the administration of investigational product, a plausible mechanism for the event to be related to the investigational product and causes other than the investigational product have been ruled out and/or the event re-appeared on re-exposure to the investigational product.

For AEs that occur prior to the administration of investigational product, an assessment of protocol relatedness must be made. Protocol-related AEs may occur as a result of procedures required during the screening process (eg, blood collection, washout of an existing medication) prior to the initial administration of investigational product. For AEs that occur before administration of investigational product, only those that are assessed by the investigator as protocol-related should be reported to the Sponsor. The following guidelines should be used by investigators to assess the relationship of an AE to a protocol-required procedure:

Protocol related: The event occurred due to a procedure/intervention that was described in the protocol for which there is no alternative etiology present in the subject's medical record.

Not protocol related: The event is related to an etiology other than the study procedure (the alternative etiology must be documented in the study subject's medical record).

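### Sections 4.1.2 and 4.4 set different thresholds for reporting non-serious events before the first dose, so a mandatory-biopsy complication with two plausible causes may be classified differently by different sites

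*Protocol*

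**What the plan says.** Four places in the Protocol govern an event that occurs after consent but before MEDI-573 is given.

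- **Section 4.1.2** covers any new untoward event in this period "which may possibly be causally related to the protocol (ie, results from a required procedure or from withdrawal of prior medication), must be reported" as an AE, on the same footing as post-dose AEs.
- **Section 4.1.1** includes protocol-related AEs in its list of AEs. It ties them to a procedure or a product discontinuation that the protocol requires, and says nothing about competing causes.
- **Section 4.4** asks the investigator to judge protocol relatedness and states that "only those that are assessed by the investigator as protocol-related should be reported to the Sponsor". There are two categories. *Protocol related* needs a procedure or intervention "described in the protocol for which there is no alternative etiology present" in the medical record. *Not protocol related* reads "The event is related to an etiology other than the study procedure", and that other etiology must be documented.
- **Section 3.6**, in the note to the screening procedures, sends new pre-dose findings that are unrelated to a protocol requirement to the baseline history or physical examination.

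Exclusion criterion 19 (section 3.1.2) and section 2.4 make a biopsy of the bladder cancer or a metastasis compulsory for every expansion subject before the first treatment, and again at the end of Cycle 1.

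**The concern.** Section 4.1.2 sets a low threshold: a possible causal link is enough. Section 4.4 sets a higher one, because a competing explanation in the record defeats the related category. Both apply to the same non-serious events in the same period.

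The difference matters most for the pre-treatment biopsy. It is a research procedure that subjects cannot decline and still enter the expansion phase, and it is done on or near a tumor that can produce similar symptoms. If sites follow different sections, the record of harm from that procedure will be uneven across the roughly 10 sites, and some of it may be recorded as a condition the subject already had.

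**Working it through.** No plan figure needs reproducing, so the check is to run one event through each rule and then count the procedures concerned.

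**Test event (illustrative, not from the Protocol).** A subject with bladder cancer has non-serious hematuria after the pre-treatment biopsy and before the first dose. The biopsy or the tumor could be the cause, and the investigator cannot tell which.

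| Rule | Test applied | Result |
|---|---|---|
| 4.1.2 | Is a causal link to a required procedure possible? | Yes, so it must be reported as an AE |
| 4.4, *Protocol related* | Due to a protocol procedure, with no alternative etiology in the record? | Fails if the tumor counts as an alternative etiology |
| 4.4, *Not protocol related* | Is it related to some other, documented etiology? | Not clearly met, because the tumor is only a candidate cause |
| 4.4, restricting sentence | Was it assessed as protocol related? | Not so assessed, so outside the events to be reported |
| 3.6 note | Is it unrelated to a protocol requirement? | If a site decides so, it becomes baseline history |

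The first and fourth rows disagree. Rows two and three show that 4.4 does not place the event in either category.

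**Does the parenthesis in 4.1.2 remove the difference?** It names two causal routes, a required procedure and withdrawal of prior medication. It adds no condition that other causes be absent, and it leaves the possibility wording in place.

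**Events outside the conflict.**
- SAEs: 4.2.2 starts the reporting period at consent, 4.2.3 requires notification whatever the presumed relationship to the product, and 7.1 requires it whatever the causality.
- Post-dose AEs: 4.1.2 requires all of them through 30 days after the last dose. The second mandatory biopsy falls after dosing, so its complications are captured.
- DLTs: 4.10 counts them from Cycle 1 Day 1.

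**Number of procedures.** There is one mandatory pre-treatment biopsy per expansion subject, and cohorts are of about 10:
- expansion halted after the first cohort: 1 × 10 = about 10
- both cohorts filled: 2 × 10 = about 20

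The count is lower if a biopsy done before consent is accepted as the screening biopsy, which the 3.6 screening note may permit. It is higher if subjects are biopsied but never dosed. The Protocol gives no complication rate, so no expected number of events can be stated.

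**The case against.** The strongest reply is that 4.4 is only guidance for a judgement that 4.1.2 already calls for. On that view the parenthesis in 4.1.2 confines it to events that result from a procedure, and 4.4 explains how to decide. An alternative etiology in the record would mean a documented cause of this particular event, not simply a known tumor. Otherwise hardly any local biopsy complication in a bladder cancer population could be called protocol related, which cannot be intended. Where 4.4 is silent, the duty in 4.1.2 still stands.

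Part of this holds. Section 4.4 leaves the dual-cause event unclassified; it does not clearly exclude it. A reader might infer that such events are barred from reporting or lost altogether. The text does not go that far, because an event judged unrelated is still recorded as baseline history under 3.6. The risk is inconsistent classification.

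The reply does not remove the inconsistency. The sensible reading of 4.4 has to be supplied by the investigator, and an investigator who charts the tumor as a possible cause still fails the related category as written.

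A reader might also infer an error from the product-relatedness scale in the same section. There, *Probable* includes "clinical status or an alternative etiology is not apparent", and for an investigator's view that is not known, "assessment is unknown or unclear, the AE is treated as product-related". Neither supports the point. *Probable* also requires an association and a plausible mechanism, and has another limb about the subject's clinical status. The default is stated for reporting to regulatory authorities. A procedure scale need not copy either.

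**Conclusion.** The point holds in limited form. Sections 4.1.2 and 4.4 can give different answers for the same non-serious pre-dose event, and 4.4 has no category that clearly fits an event with two plausible causes. Some sites may report it as an AE and others may enter it as baseline history.

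The mandatory procedures most exposed number about 10 to 20, subject to the qualifications given with that count. The conclusion assumes that at least some sites will treat a tumor that could explain the event as an alternative etiology; sites that do not will report as 4.1.2 intends.

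A reader might take this as a gap in serious-event reporting or as a threat to the dose-escalation conclusions. The documents support neither. SAEs are required from consent by 4.2.2, 4.2.3 and 7.1, and the post-dose AEs, DLTs, 3+3 rules, MTD and planned analyses do not depend on the disputed wording. It is a minor inconsistency in safety reporting, not an analysis choice. It is still worth correcting, because it concerns harm from a compulsory research biopsy.

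**What to change.** Make two edits, both in section 4.4:

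1. Define *Protocol related* as a reasonable possibility that a protocol-required procedure or medication washout caused the event, even if another etiology is also present. This agrees with 4.1.1 and 4.1.2. It also uses an approach the section already accepts for the product, where *Possible* counts as related "but there may also be alternative etiology".
2. State that the sentence restricting pre-dose reports to protocol-related events applies to non-serious AEs. This is a clarification only, since SAEs are already required from consent.

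No change to 4.2.1 or 3.6 is needed, and no visit, sample or procedure is added. The downside is a few extra screening-period AE reports for events that turn out to be due to the tumor.
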